Does the introduction of VR have an impact on patients attendance to follow up appointments: Following completion of the trial intervention period, a retrospective analysis of patients who are enrolled in the trial and require a further attendance, adherence to their follow-up appointments will be monitored. This will be completed using the department’s electronic booking system to monitor attendance. This will be compared to the department’s previous 6-month non-attendance. Data will be compared to see if enrolment on the trial and the addition of VR had any benefit in patient compliance to follow-up.

Plans to promote participant retention and complete follow-up

Participants are free to withdraw from the trial at any stage without explanation. This will be explained to them.

As participation in the trial is a relatively short amount of time, lasting only as long as their clinic appointment, we do not anticipate retention and follow-up being a significant factor in our study.

Data management

Research team members CMcF, NR, WM and LP have longstanding experience with data collection and storage. All study records and the Investigator Site File will be kept at site in a locked filing cabinet with restricted access. The Trial Master File will be held at Queen Elizabeth Hospital, Gateshead NHS trust in a locked filing cabinet with restricted access.

Data linkage will require use of NHS number which will be done securely with the IT network of Gateshead NHS Trust by a researcher with an NHS contract. The identifiable data will be stored with access restricted to the research team and will be protected by passwords. Computers will be protected by passwords and stored securely. The research team will follow guidance to ensure that personal data cannot be seen on screens or any other media by those outside the research team. Documentation including personal data will be minimal and if possible avoided and will be stored in locked cabinets in locked offices and destroyed in line with confidentiality requirements of the Trust as soon as it is no longer needed.

A pseudo-anonymised database will be prepared for analysis within the Trust for transfer for analysis at Queens University Belfast. The data for use outside the NHS will be prepared in a manner that will not allow the potential identification of individuals by combinations of data, for example, by using appropriate and ethnic group grouping that do not risk identification of individuals and anonymising all but the highest-level geographical data. Team members carrying out test accuracy and analysis will have no access to personal identifiable data.

Data generated from the research project will be stored for 10 years on NHS and/or University computers in an anonymised manner and after any patient identifiable information is removed. Access to these computers will be password protected and only by members of the research team.

Confidentiality

Confidentiality will be maintained at all times and be under the supervision of the primary investigator (VB). Members of the local site research team will have NHS

contracts with the obligation to follow all relevant NHS codes of practice and guidance. They will maintain required relevant training including NHS information governance, data security and GCP.

All participants will be allocated a number from 1-141 on their enrolment into the trial. The PI will have a separate data log to enable correlation between clinical data and study data. No other members of the team will have access to it and it will be stored on a password protected trust computer.

Questionnaires collected for analysis will be anonymous and results will be added to a password encrypted Excel, retaining the anonymity of the patients. This anonymous data will be sent via a secure link to the statisticians for analysis. No identifiable patient information will leave the hospital trust information system.

Statistical methods

Demographic characteristics will be explored for missing data and distribution abnormalities. Means and standard deviations will be used to characterise the sample. Analysis of covariance (ANCOVA) and non-parametric tests (Mann – Whitney) will be used to determine whether the VR intervention lead to a significant difference between baseline and follow up anxiety between control VR and control arm. Descriptive statistics (i.e. age, gender, ethnicity, previous attendance to colposcopy, menopausal status and parity) for the baseline values will be presented within each randomized controlled arm. P values will be used to estimate statistical significance for all analysis.

End of Study Definition

The end of study will be upon completion of the final visit of the last participant/volunteer enrolled in the trial.

Project Management Plan

PROJECT MANAGEMENT PLAN (with project milestones)			
Action	Timescale	Responsibility	Indicator / Outcome / Evidence
Develop protocol	Aug 23- Dec 23	Fellow and Supervisors	Creation of protocol to ensure robust methodology and outcome measures
Scoping exercise amongst service users	Oct 23- Dec 23	Fellow	Ensure in keeping with service users focus
Train staff on VR equipment	Oct 23 - ongoing	Fellow, Rescape	Train staff alongside Rescape to use equipment
Recruitment PPI work for patient information leaflets, questionnaires	Oct 23 - ongoing	Fellow, Research nurses	Approaching service users for feedback to ensure legibility
Begin recruitment of service users	March 24 – August 24	Fellow, Research nurses	Consenting and awareness
Begin trial and data collection	March 24 – August 24	Fellow, Research team, supervisors	Comparison of VR to standard care
Completion of data collection and writing up	Aug 24 – Dec 24	Fellow, Supervisors	Writing up analysis
Dissemination of information	Jan 25 – Aug 25	Fellow, supervisors	Conference presentations, publications

Oversight and monitoring

Composition of the coordinating centre

[name] (Principal investigator) *Clinical Research Fellow Gynaecological Oncology*

- Design and conduct of “Mind over Cervix”.
- Preparation of protocol and revisions
- Chair of steering group

- Overall responsibility for study milestones
- Preparation of case report forms (CRFs)
- Managing, monitoring and ensuring integrity of collaborative relationships

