with clear margins. Various outcomes from the examination and procedure can mean many patients are invited to reattend for a further colposcopy in a few weeks or months – such as follow up following a biopsy, unclear margins, mismatch between clinical findings and histopathological findings or the specimen being upgraded to a cancer. (5) Hence, colposcopy is often not a one stop clinic for service users so anxiety may be increasingly heightened as time progresses.

Despite colposcopy having undeniable significance in biological female's healthcare, the entire process is associated with high levels of stress and anxiety for patients. Colposcopy is a unique circumstance due to the intimate nature of the examination and the association with cancer. It is associated with fear, stress and loss of control. Many studies show that patients experience a "very high" level of anxiety when attending for colposcopy. (6) In comparison to other medical procedures, biological female patients experience a higher level of anxiety when attending colposcopy than when they are attending for cardiac surgery. (6,7) Anxiety can negatively impact a person's cognitive abilities and decreases the ability to recall and act on advice, leading to patients being less likely to comply with any information given. (8) Higher pre-procedural anxiety is predictive of post operative pain reported by patients in gynecological settings. Thus, by addressing these feelings, clinicians can reduce pain perception, however reducing this during a procedure without pharmacological agents remains a difficult task. (9)

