- There are no addition exclusion criteria as per the manufacturers instructions

Inclusion Criteria (Staff)

- Have completed colposcopy training and be a registered member of the British Society of Colposcopy and Cervical Pathology (BSCCP)
- Have completed informed consent.

Exclusion Criteria (Staff)

- The denial or withdrawal of informed consent.
- Trainee colposcopist performing clinic.

Interventions

Explanation for the choice of comparators

Biological females are offered a colposcopy appointment depending on the results of their routine cervical screening. Screening occurs every 3 years from age 25 until 49, and then 5 yearly from age 50 to 64. Cervical screening looks for HPV initially, and if this is found then cytology is performed on the specimen. If abnormal cells are found, patients are referred to colposcopy for further investigation. Here, the cervix is examined in great detail for any concerning changes. If there are areas of concern, it may require a LLETZ treatment to remove part of the cervix to prevent it from developing into cancer.

Despite the undeniable importance of colposcopy in women's' health, it is known to be a time of very high anxiety. In line with NHS values, we need to try to improve patients experience of colposcopy and try novel methods of reducing their anxiety. VR has been shown to be an effective and safe intervention in other outpatient procedures to reduce anxiety, it has not yet been investigated during outpatient colposcopy procedures. (15,18,19,20)

Intervention description

Once consented and enrolled in the trial, participants will then be asked to complete the study questionnaire (Appendix 4) which will be a paper-based format. This will allow measurement of baseline and state anxiety and anticipated pain. We will collect this data prior to randomisation of the participant into either arm of the trial. Patients will then be randomly allocated to either the VR intervention arm or the standard procedure arm. The clinician taking consent will ask the service to choose from two opaque, blank envelopes that will contain inside if they are to be enrolled in the intervention or control arm. The envelopes will be blinded to both the clinician and the patient prior to selection.

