Provisions for post-trial care Patients that are enrolled into the study are covered by indemnity for negligent harm through the standard NHS Indemnity arrangements from Gateshead health trust. Following the procedure participants will be offered the opportunity to ask the team any questions. They will be provided with contact details for the study team if they have any concerns when they have left following the procedure.

Additional patient follow up will not routinely be performed as part of the study. Any follow up will be as per standard colposcopy practice.

Outcomes

[figure not shown]
Primary outcome

- To determine any change in anxiety experienced by people with a cervix attending for outpatient colposcopy as measured by STAI (state trait anxiety index) in both the intervention arm and the control arm. Pre procedure paper questionnaires will be conducted to establish a baseline anxiety measure for patients. The comparison will be performed from the post procedure paper questionnaires from both arms of the study.

Secondary outcomes

- To determine any change in pain experience by people with a cervix attending for outpatient colposcopy as measured by a numerical rating scale (NRS) in both the intervention arm and control arm via paper questionnaires.
- Understanding the acceptability and effectiveness of VR interventions within the procedural groups and how these might vary as a function of different patient demographics.
- Feasibility and acceptance of intervention from clinicians' perspective
- Does the introduction of VR have an impact on patients' attendance to follow up appointments?

Participant timeline

Sample size

The sample size calculation was run using the packages pwr and pwrss within R. For the calculation the significance level of 0.05 and power of 0.8 were used along with a Cohen's d of 0.5. Two different types of outcome variables will be used so the calculations used are based on ANCOVA (continuous) and the Mann-Whitney test (ordinal). Both results suggest a sample size of 64 participants in each group (128 in total). We have added on a 10% drop out rate which brings the total sample size to 141.

Assignment of interventions

Sequence generation and concealment mechanism

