Participants will be randomly assigned to either control or VR intervention group by patient selection of a choice of two opaque envelopes. One envelope will instruct participant to be part of the control arm, one envelope will instruct the participant to be part of the intervention arm. The envelopes will be blinded to the researcher who provides the envelopes for the patient to choose.

Concealment mechanism Potential patients will be invited to take part in the trial prior to knowledge of what arm they will be involved in. They will be asked to complete the initial questionnaire to get a baseline STAI score before randomisation. They will be randomly allocated by patient choice of an opaque sealed envelope that will contain if they are to join the intervention or control arm. These envelopes will be blinded to the research team until after the patient selection.

Implementation All patients who consent for participation and meet the inclusion criteria will be randomized. Randomization will occur following the consent process and initial questionnaire. A member of the research team will be responsible for providing the sealed opaque envelopes for randomisation. Sealed identical opaque envelopes will be made ahead of time by the research team on a 1:1 ratio.

Assignment of interventions: Blinding

Who will be blinded?

Due to the nature of the intervention, the study team felt it is not possible to blind participants or assessors once the study arm has been allocated. Participant questionnaire results will be concealed from the assessor at point of contact.

Data collection and management

Plans for assessment and collection of outcomes

Primary outcome

Anxiety reduction: Anxiety will be measured using the state trait anxiety index (STAI) STAI was chosen as it is a well-known measure of trait and state anxiety. It is considered the “gold standard” of measuring preoperative anxiety and its reliability and validity have been well reported in literature. (33,34) State items include “I feel upset,” “I feel frightened,” “I feel nervous,” “I am jittery” and I feel confused.” Patients respond with a numerical value of 1 to 4 with 1 meaning “not at all” and 4 meaning “very much so”. (27,28)

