Participants will complete a questionnaire (Appendix 6a) with STAI questions prior to randomisation to get a baseline anxiety level. This will be compared to the post procedural questionnaire (Appendix 6b) with the same questions to compare the actual anxiety levels during the procedure. Comparison will be made between the two arms.

Secondary Outcome

Pain reduction: Pain scores will be measured by a Numeric Rating Scale (NRS) from 0 through to 10. 0 represents “no pain” and 10 represents “worst pain imaginable”. This will be shown alongside a visual analogue scale (VAS) of pain on animated faces. This is a validated measure for pain, is easy to use, has high compliance rates and detects meaningful change. (29,30,31) Participants will be asked to state the “maximum pain felt, if only for one moment,” and also state the “average pain experienced,” throughout the procedure. Respondents will select the single number that best represents their pain intensity. Results from participants in the intervention arm will be compared to participants in the control arm.

Understanding the acceptability and effectiveness of VR in variations of patient demographics: Participants will be asked to state the following demographics – age, ethnicity, parity, menopausal status, previous attendances to colposcopy and previous treatments in colposcopy. Acceptability will be monitored by participants ongoing consent of using the VR headset. If a patient removes the headset before the colposcopy assessment is completed, this will be noted in the post procedural questionnaire and be noted that the patient did not find it acceptable. The demographics of this patient cohort will be reviewed to see how VR effects different patient demographics.

Feasibility and acceptance of intervention from clinicians’ perspective: Following completion of the colposcopy assessment, the clinician will be asked to complete a short survey of their experience using VR. (Appendix 6c) These will be questions on a Likert scale from “strongly disagree” to “strongly agree”. Clinicians will be asked did they find it easy to use the VR in their clinic, did they find it beneficial to the consultation, did they find it easy to communicate with the patient during the consultation.

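### The pain outcome is worded as a change although only anticipated pain is described before the procedure, and no baseline covariate is planned for it

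*Combined protocol and SAP*

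**What the plan says.** Under Secondary outcomes, the aim for pain is "To determine any change in pain experience by people with a cervix attending for outpatient colposcopy", measured by NRS in both arms. The summary table and the abstract likewise speak of a reduction in pain.

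Intervention description sets out what is collected before randomisation: "This will allow measurement of baseline and state anxiety and anticipated pain". No item on current pain before the procedure is described.

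Plans for assessment and collection of outcomes defines the pain measure as a 0 to 10 NRS for pain during the procedure, asked once as a maximum and once as an average. It then says: "Results from participants in the intervention arm will be compared to participants in the control arm". It names no test and no covariate.

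Statistical methods applies ANCOVA and Mann-Whitney to anxiety at baseline and follow-up. It does not mention pain. The Sample size section links ANCOVA to a continuous outcome and Mann-Whitney to an ordinal one, without saying which of these is pain.

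The Background section on colposcopy states: "Higher pre-procedural anxiety is predictive of post operative pain reported by patients in gynecological settings".

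**The concern.** Two things do not fit together.

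First, a change needs a starting value of the same quantity. What a patient expects to feel is not pain she already has, so the NRS score minus anticipated pain would measure how far expectation missed experience. The data-collection section points to a different quantity, procedural pain in one arm against the other. An analyst could follow either text, and the choice would remain open after the data are seen. The choice between maximum and average pain is open in the same way.

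Second, the protocol itself says that anxiety before a procedure predicts pain. It collects that anxiety, and expected pain, before allocation, so both are legitimate covariates. Neither is given a role in the pain analysis. Pain stands in the null hypothesis, in the superiority statement under Trial design, and first among the key secondary outcomes, so its precision matters.

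**Working it through.** **Inputs from the documents**
- Error rates (Sample size): "the significance level of 0.05 and power of 0.8 were used". Sidedness is not stated. I take it as two-sided, because that reproduces 64 per arm, whereas one-sided would need 51.
- Effect size (Sample size): "along with a Cohen's d of 0.5". I apply it to pain with the SD set to 1.
- Allocation (Implementation): "Sealed identical opaque envelopes will be made ahead of time by the research team on a 1:1 ratio".
- Dropout (Sample size): "We have added on a 10% drop out rate which brings the total sample size to 141".

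**Input that is assumed**
- The correlation r between a baseline covariate and procedural pain. The documents give none. I show 0 to 0.5.

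**Step 1: reproduce the plan's figure.** A two-sided t-test with d = 0.5, alpha 0.05 and power 0.80 needs 63.8 per arm, hence 64 per arm and 128 in total. An ANCOVA whose covariate explains nothing also gives 128. Then 128 × 1.10 = 140.8, which rounds to the stated 141. The plan's size therefore counts on no gain from a covariate.

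**Step 2: adjust pain for one covariate.** Residual variance is multiplied by (1 − r²), and the standard error by √(1 − r²). Power comes from the noncentral F distribution with 1 and N − 3 = 125 degrees of freedom and noncentrality (N/4) × d² / (1 − r²). With N = 128 and d = 0.5 this is 32 × 0.25 / (1 − r²) = 8 / (1 − r²).

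| Assumed r | 1 − r² | Noncentrality | SE relative to r = 0 | Power at N = 128 | Total N for 80% power |
|---|---|---|---|---|---|
| 0 | 1.00 | 8.00 | 1.000 | 80.1% | 128 |
| 0.2 | 0.96 | 8.33 | 0.980 | 81.7% | 124 |
| 0.3 | 0.91 | 8.79 | 0.954 | 83.7% | 118 |
| 0.4 | 0.84 | 9.52 | 0.917 | 86.5% | 108 |
| 0.5 | 0.75 | 10.67 | 0.866 | 90.0% | 98 |

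The row for r = 0 shows that a useless covariate costs essentially nothing: power stays at 80.1%, as in the plain t-test. Below an r of about 0.2 the gain is negligible.

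**Step 3: two covariates together.** If anticipated pain and baseline STAI jointly explain 10%, 20% or 30% of the variance in pain, power at N = 128 is 84.1%, 88.1% or 91.8%.

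**Step 4: what the wording would cost if taken literally.** If the outcome were NRS minus anticipated pain, with equal variances assumed for the two scores, the variance would be multiplied by 2(1 − r) and the effective d would be 0.5 / √(2(1 − r)). At 64 per arm, power would be 60.2% at r = 0.2, 66.0% at r = 0.3 and 80.1% at r = 0.5. Below r = 0.5 that is worse than comparing the procedural score directly.

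**The case against.** The strongest reply is that the plan's operational text is sound. The objective is framed as an effect on pain perception against standard management, and the data-collection section compares procedural pain between arms. On that view *change* is loose wording. This largely stands. A reader might infer that the trial intends to subtract anticipated pain from the NRS score, but no section proposes it, so Step 4 shows the cost of a possible misreading and not of a planned analysis.

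Nor do the documents choose an unadjusted test. A reader might infer one from the data-collection section, but that section says only that the arms will be compared, and Statistical methods is silent on pain. The gap is an absent specification. If pain is the ordinal outcome in the Sample size section, however, its test would be Mann-Whitney, which takes no covariate.

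A reader might also infer that baseline anxiety goes unused throughout. The documents do not support that: an ANCOVA on baseline and follow-up anxiety implies that baseline STAI is the covariate for the primary outcome, even though it is not named.

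Finally, an unadjusted randomised comparison is valid, and its error rate already allows for chance imbalance. That is correct, so the issue is efficiency. It is also fair that a bounded 0 to 10 score need not be normal and that Mann-Whitney can then perform well. For that reason the comparator in Step 2 is the same linear model without covariate gain, so that the difference shown is due to the covariate alone.

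**Conclusion.** The concern holds in a limited form. The pain outcome is worded as a change that the described measurements cannot supply, and no baseline covariate is planned for it although two suitable ones are collected before randomisation. What is lost is precision on a key secondary outcome. There is no bias, the stated sample size does not depend on it, and the primary anxiety analysis is outside this point.

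For correlations of 0.2 to 0.5 the gain is about 2 to 10 percentage points of power (81.7% − 80.1% = 1.6; 90.0% − 80.1% = 9.9). This rests on d = 0.5 applying to pain, a two-sided 5% test, 64 analysed per arm and a roughly linear relation. The direction is secure, but the size cannot be derived from the documents.

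One reservation remains. A reader might conclude that no baseline pain score exists. The questionnaire appendices are not in the text available, and the data-collection section describes the first form only by its STAI questions. A current-pain item therefore cannot be excluded, and the scale of the anticipated-pain item is unknown.

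**What to change.** 1. Reword the outcome as pain during the procedure on the 0 to 10 NRS, compared between arms, and state that it is not a change from anticipated pain.
2. Name either maximum or average pain as the main score, with the other as supporting.
3. Add the pain analysis to Statistical methods: a model with arm, anticipated pain and baseline state STAI, using ANCOVA, or proportional odds if the NRS is treated as ordinal. Report the adjusted effect with its 95% confidence interval. Mann-Whitney may be kept alongside; which analysis leads is a trade-off to settle before the data are seen.
4. Confirm on the questionnaire the scale of the anticipated-pain item and whether current pain is asked.

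The cost is a change of wording and a check of the form. As described, both covariates are already collected before randomisation, so no further patients, visits or measurements are needed.
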